Duration of Exposure	5 Day MCI: Cathodal stimulation over the right DLPFC (with reference electrode on left DLPFC) will occur at 1.5mA intensity for 15 minutes over 5 consecutive treatment sessions (completed within 1 week) in participants with MCI. Cathodal stimulation over the right DLPFC (with reference electrode on left DLPFC) will occur at 1.5mA intensity for 15 minutes over 1 treatment session in participants who are cognitively unimpaired (CU) or for participants with MCI who are enrolled in the 1 Day intervention.

Statistical Methodology	
Continuous variables will be summarized as a mean <math>\pm</math> SD or median (range). Categorical variables will be summarized using number and percentage. Univariate descriptive statistics and frequency distributions will be calculated as appropriate for all variables. Stratified analysis for age in deciles will also be performed. Comparisons between sham and active tDCS (between group comparisons) will be made by one-way Analysis of Covariance (ANCOVA) method to compare the post-intervention test scores adjusting for baseline (pre-intervention) scores for the NIH Toolbox Cognition Battery (NTCB). Paired t-tests will be used for within group comparisons for NTCB scores. The NIH Toolbox Cognition Battery has six subdomains: Executive Function (NIH Toolbox Flanker Inhibitory Control and Attention Test, NIH Toolbox Dimensional Change Card Sort Test), Attention (NIH Toolbox Flanker Inhibitory Control and Attention Test), Episodic Memory (NIH Toolbox Picture Sequence Memory Test, NIH Toolbox Auditory Verbal Learning Test), Language (NIH Toolbox Picture Vocabulary Test, NIH Toolbox Oral Reading Recognition Test), Processing Speed (NIH Toolbox Pattern Comparison Processing Speed Test, NIH Toolbox Oral Symbol Digit Test), Working Memory (NIH Toolbox List Sorting Working Memory Test). Each subdomain separately, in addition to the NIH Toolbox Cognitive Function Composite Score, will be computed using the Fully Adjusted Scale score adjusted to normative data. Statistical significance will be accepted for two-sided p-values less than 0.05. To control for multiple comparison issues, p-values from pairwise comparisons will be adjusted using the false discovery rate method.

-------------------------	--

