
**Experimental Approach:**

**Accrual plan:** Participants will be identified through medical records, a flyer posted internally at Mayo Clinic Scottsdale and Phoenix, and by referrals from other Mayo physicians. The HABIT program led by [name] is very visible in the MCI community, and there exists a database of past MCI participants who may be interested in joining. Approval from the Mayo Clinic Institutional Review Board is necessary and all participants will provide written informed consent prior to participation in this study.

**Power and Sample Size Calculation:** A systematic review and meta-analysis examining effects of tDCS on cognitive function in AD shows an estimate effect size of 0.76 on outcomes similar to that of the NIH Toolbox Cognition Battery [16]; for our pilot study, a conservative estimate effect size ( $d=0.60$ ) was used due to time of

intervention. A calculated sample size of 38 (19 for each group) was derived from an ANCOVA method adjusting for pre-intervention scores with an alpha of 0.05 error, which will have 70% power to reject the null hypothesis. Thus, 38 participants (19 in each arm) will provide sufficient power. For the 5 day intervention, **we aim to enroll 44 participants with MCI total (22 in each arm), with an anticipated drop out or loss-to-follow up accounted for 10-15% in the statistical analysis to realistically achieve 19 participants per group.** For the 1 day intervention, both the cognitively unimpaired group and MCI group will be identical: we aim to enroll 44 CU participants (22 in each arm) and 44 MCI participants (22 in each arm), with an anticipated drop out or loss-to-follow up accounted for 10-15% in the statistical analysis to realistically achieve 19 participants per group.

**Sex/minority mix:** Although studies have found a higher incidence and prevalence of MCI in men, this study will strive to include 50% women [17, 18]. No discrimination or exclusion of female or minority participants will occur. Adherence to the inclusion and exclusion criteria of the study will be free of bias from race, gender, culture or religious background.

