**Exclusion Criteria:**

- Neurodegenerative disease (e.g. Parkinson's, Huntington's, Multiple Sclerosis) other than MCI
- Previous brain lesion
- Intracranial abnormality such as prior stroke
- History of seizure disorder or epilepsy
- A "true" positive response, after patient clarification, to any question on the modified TMS/tDCS Adult Safety Screen questionnaire that would impact patient safety [21] (Refer to **Appendix A**)
- Any history of brain stimulation treatment (e.g., electroconvulsive therapy (ECT), repetitive transcranial magnetic stimulation (rTMS), vagal nerve therapy (VNS), deep brain stimulation (DBS))
- Use of any investigational drug within 4 weeks
- Cardiac pacemakers, implanted medication pumps, intracardiac lines; acute or unstable cardiac disease; intracranial implants (e.g., aneurysm clips, shunts, stimulators, cochlear implants, or electrodes) or any other metal object within or near the head (exception: mouth/dental work) that cannot be safely removed
- Known or suspected pregnancy (extremely unlikely as the age range for this study is 55-85 years)

**Intervention** (independent variable): 5 Day intervention (MCI): Five consecutive weekday tDCS sessions with the Soterix tES system; 1 Day intervention (CU and MCI): 1 tDCS session. Each tDCS session will include cathode electrode placement over the right DLPFC (using the International 10-20 system) at 1.5mA intensity for 15 minutes with anode reference electrode placement over the left DLPFC. The CogState Brief Battery (One Card Learning and One Back Test) is a computerized cognitive battery that will be administered while participants undergo either active or sham tDCS stimulation. Patients who meet the inclusion criteria for the study will be randomized in a 1:1 fashion between sham and active TMS treatment. For this study, we will stratify age in deciles (55-65 years, 66-75 years, 76-85 years), as age is the number one risk factor for neurodegenerative disease. Following randomization, the patients and investigator will be blinded to the treatment group assignment and staff administering treatment will be unblinded. Refer to **Appendix B** for more information regarding device description.

Study Schedule: 5-Day MCI	Pre-Intervention		5 Day Intervention					Follow-Up
	Estimated Time	Screening & Baseline	Day 1	Day 2	Day 3	Day 4	Day 5	1 Month Follow up
Informed Consent	1 hour	x						
Eligibility Checklist 	10 minutes	x						

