will be calculated as appropriate for all variables. Stratified analysis for age in deciles and sex will also be performed. Comparisons between sham and active tDCS (between group comparisons) will be made by one-way Analysis of Covariance (ANCOVA) method to compare the post-intervention test scores between active tDCS group and sham group and adjusting for their baseline (pre-intervention) scores for the NIH Toolbox Cognition Battery. Paired t-tests will be used for within groups for ADAS-cog scores. For analysis of the NIH Cognition Battery, the same method (ANCOVA, paired t-test) will be used. NIH Toolbox Cognition Battery has six subdomains: Executive Function (NIH Toolbox Flanker Inhibitory Control and Attention Test, NIH Toolbox Dimensional Change Card Sort Test), Attention (NIH Toolbox Flanker Inhibitory Control and Attention Test), Episodic Memory (NIH Toolbox Picture Sequence Memory Test, NIH Toolbox Auditory Verbal Learning test), Language (NIH Toolbox Picture Vocabulary Test, NIH Toolbox Oral Reading Recognition Test), Processing Speed (NIH Toolbox Pattern Comparison Processing Speed Test, NIH Toolbox Oral Symbol Digit Test), Working Memory (NIH Toolbox List Sorting Working Memory Test). Each subdomain separately, in addition to the NIH Toolbox Cognitive Function Composite Score, will be computed using the Fully Adjusted Scale score adjusted to normative data. CogState Brief Battery (One Card Learning and One Back Test) will not be included in statistical analysis. Statistical significance will be accepted for two-sided p-values less than 0.05. To control for multiple comparison issues, pairwise comparisons p-values between the groups will be adjusted using the false discovery rate method.

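### The efficacy ANCOVA adjusts for baseline only and omits the age bands that appear to be randomisation strata: a minor, nearly free precision point if they are

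*Combined protocol and SAP*

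**What the plan says.** The Intervention paragraph, which follows the exclusion criteria, says that patients "will be randomized in a 1:1 fashion between sham and active TMS treatment. For this study, we will stratify age in deciles". The bands follow in the same sentence: "we will stratify age in deciles (55-65 years, 66-75 years, 76-85 years), as age is the number one risk factor for neurodegenerative disease". They are called deciles but are three bands of about ten years each. The next sentence begins "Following randomization, the patients and investigator will be blinded to the treatment group assignment".

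The between-arm efficacy test is described twice. The Statistical Methodology row of the synopsis gives a "one-way Analysis of Covariance (ANCOVA) method to compare the post-intervention test scores adjusting for baseline (pre-intervention) scores", and the Statistical analysis section gives a "one-way Analysis of Covariance (ANCOVA) method to compare the post-intervention test scores between active tDCS group and sham group and adjusting for their baseline" score. Neither puts age in the model. Both plan a separate age analysis; the synopsis says "Stratified analysis for age in deciles will also be performed", and the Statistical analysis section adds sex.

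The outcome scores "will be computed using the Fully Adjusted Scale score adjusted to normative data"; the norming variables are not listed. The Power and Sample Size Calculation rests on 19 completers per arm and d = 0.60 under a baseline-adjusted ANCOVA, "which will have 70% power to reject the null hypothesis". The same size and model serve all three cohorts.

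**The concern.** A trial that balances its arms on a factor at randomisation normally keeps that factor in the analysis model. Stratification removes the between-arm variation due to the factor. A model without the factor still counts that variation as residual error, so its standard error is too large and its test rejects too seldom under the null. At stake is a little power in a pilot planned at 70%. False positives are not inflated on either reading.

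The position of the age sentence, between two randomisation sentences, suggests that the bands are strata. It could instead be introducing the planned age-stratified analysis. The two readings call for different actions, because adding the bands is cheap only when the arms have been balanced on them.

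**Working it through.** **Inputs from the documents.** 19 completers per arm (22 enrolled), d = 0.60, two-sided 5%, power 70%, baseline as the only covariate, and three age bands (two indicator terms).

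**Inputs not given.** The pre-post correlation ρ, and the partial R² of age band after baseline. Both are assumptions here and are shown over a range.

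**Step 1: the plan's own figure.** Without a covariate, 19 per arm gives 45.6% power and 70% needs 35 per arm (normal approximation). With baseline in the model, the noncentrality is d / [√(1−ρ²) × √(2/n)] on 2n − 3 = 35 degrees of freedom. At ρ = 0.69 this is 0.60 / (0.7238 × 0.3244) = 2.555, and power is 70.0%. The stated 70% can therefore be reproduced, but only by assuming ρ of about 0.69.

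**Step 2: formula with the bands added.** The noncentrality becomes 2.555 / √(1−R²) on 33 degrees of freedom. Power is 69.9, 70.7, 72.1 and 74.3% at R² = 0, 0.02, 0.05 and 0.10. Against 70.0% the changes are -0.15, +0.7, +2.05 and +4.35 points. This assumes perfect balance on baseline and on age band.

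**Step 3: simulation.** It used 100,000 trials per setting, ρ = 0.69, 19 completers per arm, bands of 13/13/12, and a linear trend across bands scaled to the stated R². Unadjusted-for-band power is about 69% rather than 70% because the formula ignores chance imbalance in baseline.

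| Partial R² of band | 0 | 0.02 | 0.05 | 0.10 | 0.20 |
|---|---|---|---|---|---|
| Stratified: power without / with bands (%) | 68.73 / 68.29 | 69.01 / 69.35 | 69.11 / 70.80 | 69.45 / 72.95 | 70.23 / 77.61 |
| Change (points) | -0.4 | +0.3 | +1.7 | +3.5 | +7.4 |
| Stratified, 44 enrolled, 6 lost at random: change | -0.6 | +0.1 | +1.2 | +3.3 | +7.6 |
| Not stratified: power without / with bands (%) | 68.99 / 66.18 | 68.77 / 66.88 | 68.74 / 68.28 | 68.74 / 70.76 | 68.60 / 75.63 |
| Change (points) | -2.8 | -1.9 | -0.5 | +2.0 | +7.0 |
| Type I error without bands, stratified (%) | 4.94 | 4.85 | 4.56 | 3.90 | 3.00 |
| Type I error without bands, not stratified (%) | 5.06 | 4.88 | 5.09 | 4.90 | 5.03 |
| Model SE / true SD without bands, stratified | 0.996 | 0.998 | 1.015 | 1.048 | 1.107 |

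By linear interpolation, adding the bands breaks even at R² of about 0.01 if randomisation is stratified and about 0.06 if it is not.

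**Step 4: sensitivity.** Changes are at R² = 0, 0.02, 0.05 and 0.10.

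- ρ = 0.5, stratified: -0.4, +0.5, +1.8, +3.9.
- ρ = 0.8, stratified: -0.3, +0.2, +1.0, +2.2.
- Significance level 0.05/7, the strictest Benjamini-Hochberg step if the family is six subdomains plus the composite: stratified -0.6, +0.5, +2.3, +5.1; not stratified -2.8, -2.0, -0.3, +2.1.
- Unequal band shares (30/45/25%) with permuted blocks of 4 within band, ρ = 0.683, 12,000 trials per setting: -0.5, +0.45, +1.6, +3.6. Without stratification: -2.8, -1.6, -0.6, +2.2.

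**The case against.** The best case against is that nothing here is wrong. A baseline-adjusted ANCOVA is valid with or without the bands, and adding two indicators is a modelling preference. The gain is also tiny. At ρ = 0.69, moving from 19 to 20 per arm raises power from 70.0% to 72.3%, more than the 1.7 points simulated at R² = 0.05. Moving the assumed ρ to 0.67 or 0.71 shifts power to 67.8% or 72.4%, which also exceeds the effect at issue. The scores are norm-adjusted and the model already conditions on baseline, so little age signal may be left; at R² = 0 the change is a small loss. Age gets its own stratified analysis. Finally, the sample size text refers to baseline adjustment only, so an added factor would leave it slightly out of step.

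Most of this stands as to size, and it is why the point is minor. It does not remove the point. The age-stratified analysis is listed as an addition and leaves the efficacy test unchanged. If the trial does balance on age, the worst simulated cost of including the bands at the 5% level is about 0.6 points, and the change needs no new data. The mismatch with the sample size text is trivial. The Intervention paragraph should be made explicit on either answer, since both the allocation list and the analysis model depend on it.

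**Conclusion.** The point holds, as a minor precision matter and on a condition. The efficacy ANCOVA has baseline as its only covariate, while the age bands appear to be randomisation strata. If they are, including them changes power by about -0.5 to +2 points. That range assumes 38 completers, d = 0.60, ρ = 0.69, a single 5% test before any false-discovery-rate adjustment, and a partial R² of 0 to 0.05. The R² range is a judgement, plausible if the norms remove most of the age effect; at 0.10 the gain would be about 3.5 points, and 0.20 is only an upper sensitivity case. A gain is not guaranteed.

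Omitting true strata lowers the type I error (4.6% at R² = 0.05, 3.9% at 0.10), so validity is not in question. If the bands are not strata, the test without them holds its 5% level and there is no reason on this ground to change the model.

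**What to change.** First, state in the Intervention paragraph whether the age bands are randomisation strata.

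- **If they are:** write there that randomisation will be stratified by age band (55-65, 66-75, 76-85 years). In the synopsis Statistical Methodology row and the Statistical analysis section, replace the one-way ANCOVA with an ANCOVA that has treatment and randomisation age band as factors and baseline score as covariate. A matching phrase in the sample size paragraph would keep the documents aligned.
- **If they are not:** say that the bands serve only the age-stratified analysis, and leave the ANCOVA as it is.

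The cost is wording; eligibility already requires age, and the bands are already defined. The statistical price is 2 degrees of freedom. If age band is not prognostic, that is about 0.4 to 0.6 points of power under stratified randomisation, and about 2.8 points without it. The model change should therefore wait until the stratification is confirmed.

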**Feasibility and Time Frame:**

	Months 1-2	Months 3-4	Months 5-6	Months 7-8	Months 9-10	Months 11-12
Training of staff, IRB approval						
Recruitment of participants						
Data collection						
Data Analysis						
Manuscript						

## **Appendix A: tDCS/TMS Adult Safety Screen (TASS) Questionnaire:**

1. Have you ever had an adverse reaction to TMS/tDCS?
2. Have you ever had a seizure?
3. Have you ever had a stroke?
4. Have you ever had a head injury (including neurosurgery)?
5. Do you have any metal in your head (outside of your mouth), such as shrapnel, surgical clips, or fragments from welding or metalwork?
6. Do you have any implanted devices such as cardiac pacemakers, medical pumps, or intracardiac lines?
7. Do you suffer from frequent or severe headaches?
8. Have you ever had any other brain-related condition?
9. Have you ever had any illness that caused brain injury?
10. Are you taking medications?
11. If you are a woman of childbearing age, are you sexually active, and if so, are you not using a reliable method of birth control?
12. Does anyone in your family have epilepsy?
13. Do you need further explanation of TMS/tDCS and its associated risks?

\*If any question is answered in the “yes” direction, further investigate the question and seek clarification.

*(Adapted from [21] Keel JC, Smith MJ, Wassermann EM. A safety screening questionnaire for transcranial magnetic stimulation. Clin Neurophysiol. 2001;112(4):720.)*

## Appendix B: Soterix tES Device Description

[figure not shown]
### Device Description

The Soterix Medical 1x1 Low Intensity Transcranial Electrical Stimulator (tES) Model 2001 is a device that delivers low-intensity electrical current to the scalp and brain with the aim of modulating brain function non-invasively. Stimulation is applied via 2 electrodes (anode and cathode) covered by saline-soaked sponges that are held against the scalp by a pair of large, adjustable head straps. During stimulation, a small current (2mA or less) is applied to the scalp, resulting in a smaller amount of current reaching the underlying cerebral cortex. The device is powered by two 9-volt alkaline batteries.

No tDCS devices are currently FDA-approved for transcranial stimulation. tDCS devices are often determined by the FDA to constitute nonsignificant risk in research protocols.

The stimulator is comprised of a small control box (length 7.91 in., width 5.9 in., height 2.83 in.) that contains the power source (2 9-volt alkaline batteries), displays (actual current delivered, impedance/contact quality, stimulation time remaining, low battery indicator), and controls (power, current intensity, stimulation duration, stimulation “start,” and emergency abort). The device’s maximum output voltage is 40V +/- 5%, and maximum output current is 2mA DC +/- 1%.

Pictures below depict the tDCS device (1x1 tES), electrodes and sponges, and representative illustration of participant wearing the device.

## Appendix C: Anticipated Risks

There is ample literature supporting the safety of tDCS, including several systematic reviews. Brunoni et al. (2011)[22] reviewed 209 tDCS studies, the majority of which involved healthy control adult participants and single-session tDCS; of these, 74 studies (with 1851 participants) included reporting of AEs. The authors noted that tDCS appeared well-tolerated overall, with relatively mild AEs (scalp itching in 39.3%; tingling sensations, 22.2%; headache, 14.8%; scalp discomfort, 10.4%; burning sensations, 8.7%) in those receiving active tDCS, and with no difference in AE rates between those receiving active and sham treatments. Aparicio et al. (2016)[23] presented an updated systematic review of 64 randomized controlled trials (2262 participants) whose protocols involved five or more treatment sessions. By contrast, the majority of studies included in this review consisted of samples with neurologic and psychiatric conditions. Participants receiving active tDCS did not drop out of studies at higher rates than those receiving sham, and nearly half of studies reported no dropouts, indicating good acceptability of tDCS over multiple sessions. Another recent review by Bikson and colleagues (2016)[24] notes that over 33,200 sessions of tDCS have been performed in human participants across a range of treatment parameters, without any serious adverse events (SAEs) or evidence of irreversible injury reported.

**Seizures: No reports have been published of seizures following tDCS at the rate and strength of the stimulation in this study.** However, individuals who have a history of epilepsy or have had a seizure during the last 12 months will be excluded from this research study.

### Seizure management plan and precautions to ensure safety of participants

A “help” pull cord is available in the treatment room, and access to life-support equipment and antiepileptic drugs are accessible. Furthermore, a clinician trained in seizure management will be on the same floor as the treatment room, and are readily available. In management of seizures, attention must be taken to minimize the risk of aspiration, and when possible, guiding the patient into the left lateral decubitus position is desirable. Because most seizures are brief (typically <60 seconds) and without serious physical sequelae, efforts will be focused on preventing complications of the seizure rather than initiating any specific medication that is not required unless a seizure is prolonged. If a prolonged seizure (>60 seconds) is identified, appropriate response measures will be initiated which may include notifying a hospital-based rapid response team and/or escorting patient to the nearest emergency department upon stabilization. If a seizure occurs during the active treatment phase of the study, active treatment as part of the study will be discontinued. Ongoing monitoring of neurocognitive symptoms per the study protocol will be offered.

### Other potential side effects of tDCS that may be experienced *during* treatment

- **Skin Irritation:** There is a risk of mild skin irritation at the location where the electrode sensors have been placed, but this usually consists of minor redness that will go away quickly after they are removed. Localized tingling sensation, itching, skin erythema, scalp discomfort, and burning sensations have also been reported equally in active and sham tDCS and resolve after treatment.
- **Headache:** A mild headache can occur following tDCS treatment that usually resolves soon after the procedure. We will try to reduce the risk of headache by assuring the participant’s comfort before and during the procedures.

